### 3.1 Sample Size & Power

- Planned Enrollment: Based on the study proposal and prior pilot data, at least 20 residents per site across eight sites (n=160 residents) were planned for recruitment. Staff participants were included according to the number of residents assigned to them (2–6 residents per staff participant).
- Power Analysis: The study was powered to detect small-to-moderate effect sizes (Cohen's d = 0.35-0.40) for paired t-tests on primary outcomes with 80% power and a two-sided  $\alpha = 0.05$ , assuming 20–25% attrition.
- Baseline Assessments: Demographic variables and cognitive status (MMSE) were collected at baseline. Descriptive analyses will summarize these characteristics for residents and staff.

## 3.2 Actual Analyzed Sample

- Residents: 107 participants included in final analyses.
- Staff: 53 participants included in final analyses.

## 3.3 Randomization / Masking

 The study did not include randomization or blinding due to feasibility and practical considerations.

## 3.4 Analysis Populations

- Intention-to-Treat (ITT): All participants with baseline and at least one post-intervention measure. ITT analyses will use mean substitution for missing items within allowable thresholds (≤50% missing per scale).
- Per-Protocol (PP): Participants completing baseline and 4-week follow-up without major protocol deviations. Analyses restricted to this population will serve as sensitivity analyses.

#### 4. Outcomes

## 4.1 Primary outcome (Residents & Staff)

	Title	Description of Primary Outcome Measures
1	Change in Center for	10-item Measure of depressive symptomatology; Scale: 0 (rarely
	Epidemiological	or none of the time) to 3 (most or almost all of the time);
	Studies Depression	Possible scores range from 0 (minimum) to 30 (maximum).
	Scale (CES-D)	Higher scores indicate higher frequency of reported depressive
		symptomology.
2	Change in Satisfaction	Measurement of resident satisfaction with care in a long-term
	With Care in the	care facility; 8-items measured on a scale of 1 = generally yes
	Nursing Home Scale	and 0 = generally no; Possible scores range from 0 (minimum) to
		8 (maximum). Higher scores indicate higher satisfaction with
		care at the resident's facility.
3	Change in Quality of	13-item Quality of life scale for an individual living with
	Life Alzheimer's	Alzheimer's Disease: rated on a scale of 1 (poor) to 4 (excellent);
	Disease (QoL-AD)	Possible scores range from 13 (minimum) to 52 (maximum).
		Higher scores indicate higher quality of life.
4	Change in Cohen-	14-item Measurement of agitation that was completed by the
	Mansfield Agitation	staff for each resident they were assigned to conduct a life story
	Inventory (CMAI) - Short	interview with at baseline and post-intervention (proxy
	Form From Baseline	completed by staff on behalf of each resident) rated on a scale:
		1 (never) to 5 (several times an hour) scores can range from 14-
		70, with higher scores indicating higher frequency of agitated
		behaviors of persons living with dementia as reported by those
		staff conducting their life story interviews.
5	Change in Staff	Measurement of the attitudes of long-term care staff towards
	Attitudes Towards	the residents under their care includes 4-items on a 5-pt scale
	Residents Scale From	of 1= never to 5=always, scores ranging from 4 to 20, higher
	Baseline	scores indicate more positive attitudes toward residents.
6	Change in	13-item subscale of the ICI scale "knowing the person"; rated on
	Individualized Care	a scale from 1 (strongly disagree) to 4 (strongly agree); Possible
	Instrument (ICI)	scores range from 13 (minimum) to 52 (maximum). Higher
		scores indicate staff feel they know the resident(s) more.

	ı	
	Subscale - Knowing the Person - From Baseline	
7		3-item Measurement of feelings of loneliness; rated on a scale:
/	Change in The UCLA 3- Item Loneliness Scale	
	From Baseline	1 (hardly ever) to 3 (often), ranging from 3 to 9, higher scores
		indicate higher feelings of loneliness.
8	Resident Satisfaction	A total of 9-items were developed from the pilot and current
	With the LifeBio	study to understand residents' acceptance and satisfaction
	Memory Program	with the LifeBio Memory program. Participants answered either
		"no" (0) or "yes" (1) to each item, with total scores ranging from 0
		to 9 (higher scores indicating high satisfaction with the LifeBio
		Memory program).
9	Change in Perceived	A 3-item measure related to the importance of life story work
	Importance of Life	with residents; items are rated on a scale from 1 = strongly
	Story Work Among Staff	disagree to 5 = strongly agree, scores ranging from 3 to 15, with
		higher scores indicating staff feeling life story work is more
		important.
10	Staff Satisfaction With	On the follow-up post-evaluations, staff were asked to rate their
	LifeBio Memory	overall satisfaction with the LifeBio Memory program. A total of
	Program	8-items developed from the pilot and current study were rated
		on a 1 (strongly disagree) to 5 (strongly agree) scale. Possible
		scores range from 8 (minimum) to 40 (maximum). Higher scores
		indicate higher satisfaction with the program.
11	Change in Sense of	17-item measurement of staffs' overall sense of dementia care
	Competence in	competence; rated on a scale: 1 (not at all) to 4 (very much) with
	Dementia Care Staff	scores potentially ranging from 17-68, higher scores indicating
	(SCIDS) Scale From	higher sense of competence in dementia care among staff.
	Baseline	
12	Change in Person-	10-item measurement of staff experience with person-centered
	Centered Care	care in their current care community; rated on a scale: 1
	Assessment Tool [Sub-	(strongly disagree) to 5 (strongly agree), scores ranging from 10-
	Scales I and II] From	50, higher scores indicating higher agreement with experience
	Baseline	providing person-centered care.
13	Change in Direct Care	9-item measurement of staff satisfaction with different aspects
	Worker Job Satisfaction	of their job; rated on a Scale: 1 (very dissatisfied) to 4 (very
	Scale From Baseline	satisfied), potential scores ranging from 9-36, higher scores
		indicating higher satisfaction with their job.
14	Change in	15-item Measurement of staff perceptions about resident's
	Individualized Care	autonomy; rated on a Scale: 1 (never) to 5 (very frequently),
	Instrument (ICI)	potential scores ranging from 15-75, higher scores indicating
	Subscale - Resident	staff perceiving residents having more frequent autonomy.
	Autonomy Subscale -	
	From Baseline	
15	Change in	7-item measurement of staff perceptions of their
	Individualized Care	communication with residents; rated on a Scale: 1 (never) to 4
	Instrument (ICI)	(always), scores ranging from 7-28. higher scores indicating
	Subscale - Staff and	higher frequency of staff to resident communication about their
	Resident	care.

	Communication	
	Subscale - From	
	Baseline	
16	Change in Individualized Care Instrument (ICI) Subscale - Staff to Staff Communication Subscale - From Baseline	10-item measurement of staff perceptions of staff to staff level communication, rated on a scale from 1 (never) to 4 (always), scores ranging from 10-40, higher scores indicating more frequent staff to staff communication.
17	Staff Perceptions About the Feasibility of the LifeBio Memory Program Protocol	7-items were developed (rated on a 1 = strongly disagree to 5 = strongly agree response scale) and administered on the follow-up post-evaluation to understand staff's perceptions about the feasibility of the program protocol once interviews were complete and materials (i.e., Action Plans, Life Story books, Snapshots) were delivered (e.g., Within the first 2-weeks of delivery, I was able to present the residents' Action Plans during a team meeting"). Possible scores range from 7 (minimum) to 35 (maximum). Higher scores indicate higher feasibility with the implementation of program materials.

## 4.2 Secondary outcomes (Residents & Staff)

MMSE, Staff knowledge of resident life stories and care preferences.

	Title	Description of Secondary Outcome Measures
18	Change in Mini Mental	Screening for resident cognitive status, scores can range from 0-
	Status Examination	30, lower scores indicate more cognitive impairment (higher
	(MMSE) From Baseline	scores indicate less cognitive impairment).
19	Change in Staff	1-item asked of staff for each resident they interviewed on a
	Adequate Knowledge of	scale of 1 = not at all well, to 5 = extremely well ("How well do
	Residents' Care	you know the resident's care preferences?")
	Preferences From	
	Baseline	
20	Change in Staff	1-item asked of staff for each resident they interviewed on a
	Adequate Knowledge of	scale of 1 = not at all well, to 5 = extremely well ("How well do
	Residents' Life Stories	you know the resident's life story?")
	From Baseline	

## 4.3 Other Prespecified (Staff)

	Title	Description of Other Pre-specified Outcome Measures
21	Length of Time Staff	Item related to staff time spent on LifeBio Memory training
	Spent on LifeBio	
	Memory Training	

22	Preparedness Of Staff Conducting Life Story Interviews	Staff self-rated preparedness to conduct life story interviews with residents and set up their accounts following training; two 1-item survey questions rated on a scale from 1 = strongly disagree to 6 = strongly agree. Higher score on each item means stronger agreement towards feelings of being prepared to conduct a life story interview with a person living with dementia using the LifeBio Memory app and setting up their account using the LifeBio Memory app.
23	Staff Training Needs Being Met With LifeBio Memory Training	Staff overall feelings of needs being met with the LifeBio Memory Training Program. Staff were asked, "Overall, how well does the LifeBio Memory App training meet your needs?" On a scale from 1 = not well at all to 5 = extremely well.
24	Staff Objective Knowledge of LifeBio Memory Training Content	Staff completed an 11-item quiz post-training (tested on content detailed in the training videos). It was a multiple choice type quiz, and average score represents total number of correct items on the quiz. Scores could range from 0 to 11, with the staff ranging from 5-items correct to 11-items answered correctly. Higher scores indicate higher number of quiz items answered correctly.

### 5. Statistical Considerations

All analyses will follow a prespecified Statistical Analysis Plan and adhere to best practices for exploratory behavioral and clinical research. Analyses will be conducted in SPSS (Version 28.0.1.1), with syntax retained to ensure reproducibility. Statistical tests will be two-sided at  $\alpha$  = 0.05, with 95% confidence intervals reported alongside p-values. Given the exploratory nature of the study and multiple outcomes, effect sizes (Cohen's d for t-tests, partial  $\eta^2$  for ANOVA, Pearson's r for correlations) will be emphasized in interpretation.

Primary analyses will focus on pre - post changes within residents and staff, with paired-samples t-tests used for continuous outcomes and descriptive summaries for program-specific measures. Secondary and exploratory analyses will include additional intervention specific and knowledge outcomes, as well as subgroup analyses when applicable. For all parametric tests, assumptions of normality, homogeneity of variance, and linearity will be assessed, and nonparametric alternatives will be applied if assumptions are violated.

Finally, due to the exploratory study design, no formal multiplicity correction will be applied. However, results will be interpreted with caution, emphasizing consistency across outcomes and practical/clinical significance. Transparency will be maintained by reporting all prespecified outcomes, documenting handling of missing data, and providing effect sizes alongside inferential statistics.

## 5.1 General Principles

All statistical analyses will adhere to standard practices for clinical and behavioral research and will be conducted in a reproducible and transparent manner.

#### 5.1.1 Analysis Software

- All analyses will be performed using IBM SPSS Statistics Version 28.0.1.1.
- Syntax will be retained to ensure reproducibility.

#### 5.1.2 Significance Level and Confidence Intervals

- All hypothesis tests will be two-sided with a significance threshold of  $\alpha$  = 0.05, unless otherwise justified (e.g., exploratory analyses).
- 95% confidence intervals (CIs) will accompany point estimates for all primary and secondary outcomes to convey precision.

#### 5.1.3 Effect Sizes

- Effect sizes will be reported for all inferential analyses to complement p-values and provide practical significance:
  - o Cohen's d for paired or independent-samples t-tests
  - Partial η for ANOVA or repeated measures designs
  - o Pearson's r for correlations
- Effect size interpretation will follow conventional thresholds (small, medium, large) and be considered in context of the exploratory nature of the study.

#### 5.1.4 Analysis Populations

 Complete-case: Analyses restricted to participants with no missing data on the outcome of interest.

#### 5.1.5 Assumptions and Model Checks

- For parametric tests (t-tests, ANOVA, Pearson correlations), assumptions of normality, homogeneity of variance, and linearity will be evaluated using:
  - Shapiro-Wilk test and Q-Q plots (normality)
  - Levene's test (homogeneity of variance)
  - Scatterplots (linearity for correlations)
- If assumptions are not met, appropriate nonparametric alternatives will be considered (e.g., Wilcoxon signed-rank test, Spearman correlations).

#### 5.1.6 Interim Analyses

• No interim analyses are planned due to the exploratory and short-duration nature of the LifeBio Memory project.

#### 5.1.7 Reporting Conventions

- All results will include sample sizes (n), descriptive statistics (mean, SD, median, IQR as appropriate), p-values, 95% CIs, and effect sizes.
- Any deviations from the pre-specified analyses will be documented and justified.

## 5.2 Missing Data

Procedures for handling missing data will follow published guidelines for patient-reported outcome (PRO) measures and psychometric scales.

- Item-level missingness for composite scales:
  - o If a participant is missing more than 50% of the items on a given measure, no total score will be calculated and the case will be excluded from that outcome analysis.
  - o If less than 50% of items are missing, the participant's total score will be calculated using mean substitution at the item level. Specifically, the individual's mean score across available items will be imputed for missing items, and the total score will be computed based on the expected number of items in the scale.
  - This approach is consistent with recommendations for handling missing items in multi-item questionnaires where internal consistency is expected (Enders, 2010; Fayers & Machin, 2016).
- Examples of application in this study:
  - UCLA Loneliness Scale (3-item short form): If 2 or more items are missing, no total score will be calculated. If 1 item is missing, the mean of the two available items will be substituted.
  - Resident Satisfaction with Care Scale (8 items): If ≤3 items are missing, the individual mean will be substituted for missing items; otherwise, the score will not be calculated.
  - o Quality of Life–AD Scale (13 items): If ≤6 items are missing, mean substitution will be applied; otherwise, the score will not be calculated.
  - CES-D 10-item form: If ≤5 items are missing, mean substitution will be applied;
     otherwise, the score will not be calculated.
- Dataset-level handling:
  - No advanced imputation methods (e.g., multiple imputation, maximum likelihood)
     are planned due to the modest sample size and exploratory nature of the project.

#### Documentation:

- All imputation procedures will be implemented in SPSS using standard syntax with explicit commands.
- All decisions about missing data will be logged, and final datasets will be archived with accompanying metadata to preserve transparency.

## 5.3 Descriptive Statistics

- All study variables will first be summarized descriptively to characterize the sample and provide context for subsequent analyses.
- Continuous variables (e.g., age, MMSE scores, CES-D, QoL-AD) will be summarized using means, standard deviations (SDs), medians, interquartile ranges (IQRs), and ranges, as appropriate. Normality assumptions will be assessed visually (histograms, Q–Q plots) and statistically (Shapiro–Wilk test).
- Categorical variables (e.g., gender, education) will be reported as counts and percentages.
- Baseline characteristics will be summarized separately by participant type (resident, staff), and group-level comparisons will be presented descriptively only (i.e., no inferential tests for baseline balance given the non-randomized design).

## 5.4 Primary Analyses

- The primary analyses will evaluate pre–post changes within residents and staff across the outcomes of interest.
  - Residents: Paired-samples t-tests will be conducted comparing baseline (T1) and 4week (T2) scores for:
    - Center for Epidemiologic Studies Depression Scale (CES-D)
    - Quality of Life in Alzheimer's Disease (QoL-AD)
    - Cohen-Mansfield Agitation Inventory (CMAI)
    - Loneliness scale
    - Satisfaction with Care measure
  - Staff: Paired-samples t-tests will be conducted comparing baseline and 4-week scores for:
    - Staff attitudes toward persons living with dementia
    - Dementia care competence
    - Job satisfaction
    - Individualized Care Inventory (ICI) subscales
    - Person-Centered Care Assessment Tool (PCCAT)
  - Program-specific outcomes: Descriptive statistics and paired-samples t-tests will summarize outcomes related to satisfaction with the LifeBio program, feasibility of implementation, and training outcomes (e.g., perceived preparedness, confidence in using LifeBio).
  - For all paired *t*-tests:
    - Results will be reported as mean differences with standard deviations, tstatistics, degrees of freedom, p-values, and 95% confidence intervals.
    - Effect sizes (Cohen's d) will also be reported.
  - In cases where normality assumptions are substantially violated, nonparametric alternatives (Wilcoxon signed-rank test) may be considered and reported as sensitivity analyses.

## 5.5 Secondary Analyses

- Secondary analyses will explore additional outcomes not designated as primary but still relevant to the LifeBio Memory project.
  - Residents: Mini-Mental State Examination (MMSE) scores will be analyzed using paired-samples t-tests (baseline vs. 4 weeks).
  - Staff: Knowledge of resident life stories and personal preferences will be analyzed using paired-samples t-tests.
  - Exploratory analyses: Where appropriate, subgroup analyses (e.g., stratification by site) will be conducted to explore heterogeneity of effects. These analyses will be treated as exploratory and interpreted with caution.
- Results will be reported consistently with the primary analyses, including p-values, 95% confidence intervals, and effect sizes.

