## 5.6 Multiplicity

- Given the exploratory nature of this project and the inclusion of multiple outcomes, formal adjustment for multiplicity (e.g., Bonferroni or Holm corrections) will not be applied. Instead, the following principles will guide interpretation:
  - Primary vs. Secondary Outcomes: If designated, primary outcomes will be the main focus of interpretation. Secondary outcomes and subgroup analyses will be considered hypothesis-generating.
  - Subgroup and Sensitivity Analyses: Comparisons across subgroups (e.g., completers versus non-completers, site-level differences) will be viewed as exploratory and interpreted cautiously.
  - Interpretation Strategy: Results will be evaluated in terms of effect sizes, 95% confidence intervals, and the consistency of findings across related measures, with attention to clinical and practical significance.
  - Transparency: All pre-specified outcomes will be reported regardless of statistical significance to minimize selective outcome reporting.

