## 8.2 Planned Tables, Figures, and Listings (TFLs)

The following tables and figures will be included in study reports and publications:

- Participant Flow: A CONSORT-style diagram summarizing enrollment, exclusions, intervention completion, and analysis populations (staff and residents).
- Baseline Characteristics: Tables summarizing demographics, cognitive/functional characteristics, and relevant staff/resident attributes by study group.
- Pre-Post Outcomes: Summary tables of primary and secondary outcomes, reporting means, standard deviations, sample sizes, p-values, and effect sizes (Cohen's d).
- Subgroup Analyses: Where applicable, outcomes stratified by relevant subgroups (e.g., completers of the intervention versus non-completers).
- Supplementary Figures: Graphical displays of key outcomes over time (e.g., line graphs, bar charts).

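### Site differences are to be explored by stratifying with p-values and no between-site test, which at about 13 residents per site will usually look mixed even if every site has the same effect

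*Combined protocol and SAP*

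**What the plan says.** SAP 2.2 sets an exploratory objective of looking for subgroup differences, with staff role and site as its examples. The method is in 5.5: "subgroup analyses (e.g., stratification by site) will be conducted to explore heterogeneity of effects". That sentence is conditional on the analysis being appropriate. It is followed by "These analyses will be treated as exploratory and interpreted with caution" and "Results will be reported consistently with the primary analyses, including p-values, 95% confidence intervals, and effect sizes". The primary analyses in 5.4 are paired t-tests of baseline against four weeks.

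Section 5.6 states that "formal adjustment for multiplicity (e.g., Bonferroni or Holm corrections) will not be applied" and that "Comparisons across subgroups (e.g., completers versus non-completers, site-level differences) will be viewed as exploratory and interpreted cautiously". It bases interpretation on effect sizes, confidence intervals and consistency across measures.

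On numbers, 3.1 planned "at least 20 residents per site across eight sites" and 3.2 gives "Residents: 107 participants included in final analyses", with 53 staff. Neither the number of sites analysed nor the count per site is stated.

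On completion, 5.7 compares completers and non-completers on baseline variables only. The list of tables in 8.2 goes further and includes "outcomes stratified by relevant subgroups (e.g., completers of the intervention versus non-completers").

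**The concern.** A paired t-test inside one site asks whether that site changed. It does not ask whether sites differ. To read heterogeneity from a set of such tests is to compare significant with non-significant results, and in small strata that contrast is driven mainly by chance. The exploratory objective could then be answered with a statement that the programme worked at some sites and not at others, when the data are fully compatible with one common effect. ANOVA and partial eta-squared appear in 5 and 5.1.3, but only as general conventions; nothing ties them to site or staff role.

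The completion split in 8.2 is a different matter. Completion is known only after baseline, and a participant with no follow-up score has no change to tabulate. The ITT definition in 3.4 already requires at least one post-intervention measure. Sections 5.7 and 8.2 therefore describe different analyses of the same grouping.

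**Working it through.** **Inputs.** Eight planned sites, at least 20 residents each, d = 0.35–0.40, paired t-test, 80% power, two-sided alpha 0.05, 20–25% attrition (SAP 3.1); 107 residents and 53 staff analysed (3.2). Assumption: all eight sites contribute, in about equal numbers.

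**1. The plan's own figure.** 20 × 8 = 160. By noncentral t, 80% power needs 67 pairs at d = 0.35 and 52 at d = 0.40. With attrition: 67/0.80 = 84 and 67/0.75 = 90; 52/0.80 = 65 and 52/0.75 = 70. The 160 is therefore sites times residents, not the output of the stated power inputs. This does not affect the present point. With 107 pooled pairs, power is 95–98% and the detectable d at 80% power is 0.27.

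**2. Residents per site.** 107/8 = 13.4, for example five sites of 13 and three of 14 (65 + 42 = 107).

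**3. Power in one site.** With n = 13, df = 12, the critical t is 2.179 and the noncentrality is d√n.
- d = 0.35: 0.35 × 3.606 = 1.262; power 0.2135.
- d = 0.40: 0.40 × 3.606 = 1.442; power 0.2643.

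For 80% power a site would need d of about 0.85 (0.81 with 14 residents).

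**4. Chance of a mixed picture under one common effect.** P(mixed) = 1 − p⁸ − (1 − p)⁸, where p is the power per site and p⁸ is negligible.
- d = 0.35: 1 − 0.7865⁸ = 1 − 0.146 = 0.854; expected significant sites 8 × 0.2135 = 1.7.
- d = 0.40: 1 − 0.7357⁸ = 1 − 0.086 = 0.914; expected significant sites 8 × 0.2643 = 2.1.
- No effect, p = 0.05: 1 − 0.95⁸ = 1 − 0.663 = 0.337.

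**5. If the number of sites is not eight.**

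| Sites | Residents per site | Mixed, d = 0.35 | Mixed, d = 0.40 | Mixed, d = 0 |
|---|---|---|---|---|
| 6 | 18 | 87% | 93% | 26% |
| 8 | 13 | 85% | 91% | 34% |
| 9 | 12 | 86% | 92% | 37% |
| 12 | 9 | 86% | 91% | 46% |

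**6. Simulation.** 40,000 trials with five sites of 13, three of 14 and the same true effect everywhere gave a mixed pattern in 86% (d = 0.35), 92% (d = 0.40) and 34% (d = 0). One-way ANOVA of change scores by site rejected in 5.0% at each of these effects. At d = 0.35–0.40 the median gap between the largest and smallest site d was about 0.85, and at least one site pointed the wrong way in 57% down to 45% of trials.

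**7. Staff outcomes.** 53/8 = 6.6, so six or seven staff per site. Power per site is 11–15%, and a mixed pattern appears in 60–72%.

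**8. What the single test can detect.** Let true site effects vary with SD τ, in units of the within-site SD of change. The F ratio is then about (1 + 13.4τ²) times a central F on 7 and 99 df, whose critical value is 2.10.
- τ = 0.2: 2.10/1.535 = 1.37; power about 23%.
- τ = 0.3: 2.10/2.204 = 0.95; power about 47%.

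**The case against.** The strongest reply is that the SAP does not prescribe what is being criticised. A reader might infer that separate per-site tests are mandated. They are not: stratification is given as an example, made conditional on being appropriate, and 5.6 speaks of comparisons across subgroups, which is between-group language. The per-site paired test follows only from combining stratification with the instruction to report as in the primary analyses. This stands as a limit on the wording. The gap remains, because no passage names a between-site contrast for the objective in 2.2.

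The second reply is that 5.5 and 5.6 call for caution and for reading effect sizes and intervals rather than sorting sites by p < 0.05. That reduces the harm, and is why the point is minor. It does not supply a test of heterogeneity, and site effect sizes read by eye are no safer: step 6 shows a typical spread of about 0.85 when nothing differs.

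The third reply is that the replacement test is weak. This also stands (step 8). It controls false signals of difference but will often miss real ones, and the SAP should say so.

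**Conclusion.** The point holds as a minor one. As written, the site analysis has no method that answers its own question. At about 13 residents per site, a common effect of the size planned for would produce apparent disagreement between sites in 85–91% of cases per outcome, against about 5% for a single between-site test. The result rests on roughly equal site sizes, on eight contributing sites (6–12 sites give 85–93%), and on independence between residents. Residents who share a staff member, 2–6 each, may be correlated, which the calculation ignores.

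Some stronger readings are not supported:
- That misleading site differences are certain. The 85–91% requires a true d of 0.35–0.40 everywhere; with no effect the figure is 34%.
- That the completion split creates site differences. It cannot; it is a separate inconsistency between 5.7 and 8.2.
- That non-completers mostly lack follow-up, or differ for reasons unrelated to the programme. The documents give no counts or reasons, and a resident may miss part of the intervention and still be assessed.
- That false positives can be counted by multiplying sites by every listed change outcome. This mixes resident and staff outcomes, whose numbers per site differ.

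**What to change.** In SAP 5.5, replace stratified p-values with one model per outcome: change score on site, or a random site effect. Report one heterogeneity test, and show site estimates with 95% confidence intervals, for example as a forest plot, without per-site p-values. Specify the same for staff role. Add a sentence that the test has limited power, so a non-significant result does not show that sites are alike.

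Reconcile 5.7 with 8.2. Either remove the outcome tables split by completion, or keep them and label them descriptive, stating that completion is a post-baseline event and that participants without follow-up contribute no change score.

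The cost is close to nil: the same data, a model available in the stated software, a few sentences of text and fewer tests to report.
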